6.2. Secondary objectives

1. Assess morbidity of metastatic RCC including
 - a. co-diagnoses and procedures
 - b. infections and antibiotic use
 - c. antihypertensive use before and after mRCC diagnosis, as applicable

2. Assess speciality care healthcare resource use (absolute, per patient, per patient year)
 - a. cumulatively over time from diagnosis
 - b. by treatment line

6.3. Exploratory objective

1. Assess changes in coding practices over time, specifically IMDC risk score
 - a. including but not limited to changes in structured IMDC score recordings and the use of metastatic ICD-10 diagnosis codes (C77-C79)

7. RESEARCH METHODS

7.1. Study design

This is a retrospective registry-based cohort investigation, utilizing existing data generated during routine clinical practice and available in the Hospital District of Southwest Finland HDSF data lake. All adult patients (age ≥ 18 years) with RCC diagnosis (C64*; '*' indicates any number) will be identified from the data lake of HDSF.

The main purpose of this study is to characterize the patient population of advanced/metastatic RCC, and their treatment patterns and treatment outcomes using medical records retrieved from HDSF data lake. The main patient stratification will be the IMDC risk category (see 8.2.3 Patient stratification). Patients with unknown risk score will be analyzed as an own patient group.

7.2. Setting

The target population of this study is adult patients with RCC and medical records available at HDSF data lake. Estimated number of patients in this study is 220-550. The inclusion criteria is a diagnosis of renal cell carcinoma (ICD-10: C64) between January 2010 and December 2021 (Figure 1). Advanced/metastatic disease stage (mRCC) will be assessed based on ICD-10 diagnosis code for metastasis (C77*-C79*), American Joint Committee on Cancer (AJCC) stage 4, visit to oncologist (specialty code 65), or initiation of treatment for mRCC.

[figure not shown]

Figure 1. Graphical illustration of study time windows and corresponding analyses.

The data collected has been generated as part of standard clinical care, treatment, and follow-up of patients with RCC. In accordance with the Finnish Act on Secondary Use of Health and Social Data 552/2019 (in Finnish: Laki sosiaali- ja terveystietojen toissijaisesta käytöstä), health registry data can be processed in scientific studies without patient consent. The purpose of this act is to establish conditions for the effective and secure processing of, and access to, personal health and social data for certain secondary purposes, such as research and statistics, innovation and development, knowledge management, teaching and authority planning. Thus, the Secondary Act creates a clear legal basis for the use of such registered data for research and innovation related to, for example, the health and well-being of citizens, the prevention of

disease and the development of new treatment methods. This relatively new legislation is also a welcome unification of the fragmented Finnish national rules regarding the use of healthcare and social welfare data. In addition, it takes into consideration current data protection requirements.

In the primary objective 1 (characteristics), all RCC patients will be analysed (local and metastatic diseases separately), while in the other objectives only treated mRCC patients will be analysed. Therefore, there are two cohorts to be analysed: 1) characteristics cohort (including all RCC patients), 2) mRCC cohort (including only treated mRCC patients).

Definitions for mRCC cohort

Index: Date of the first mRCC diagnosis; date of the metastatic disease identified as first of the following after the initial RCC diagnosis

- ICD-10 diagnosis code (C77*-C79*) for metastatic disease
- AJCC stage 4
- Visit to oncologist (specialty code 65) with RCC as main diagnosis
- Treatment initiation for mRCC (sunitinib, pazopanib, cabozantinib, ipilimumab, nivolumab)

When analyzing the treatment outcomes, index is defined as the date of the treatment initiation.

End of follow-up (whichever of the following occurs first):

- Death
- Moving outside of HDSF
 - Approximated using data of healthcare contacts; no contacts to specialty care of HDSF within 2 years (patient censored at the last recorded visit)
- End of study (31.12.2021)

Length of follow-up (in years): ('end of follow-up' – 'index' + 1)/365.25

Definitions for characteristics cohort

Index:

- For mRCC patients, same as for the mRCC cohort (i.e. approximated metastasis date)
- For RCC patients, the date of the first record of RCC diagnosis (ICD-10: C64)

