7.2.1. Inclusion criteria

For the **characteristics cohort**, patients must meet all of the following inclusion criteria to be eligible for inclusion:

- Diagnosis of renal cell carcinoma (ICD-10: C64) during 1.1.2010-31.12.2021
- Age at least 18 years at index.
- Resident of HDSF at index.

For the **mRCC cohort**, patients must meet the following inclusion criteria in addition to the above criteria to be eligible for inclusion:

- metastatic RCC during 1.1.2010-31.12.2021; defined as
 - ICD-10 diagnosis code for metastasis (C77*-C79*), or
 - AJCC stage 4, or
 - AJCC stage data potentially not available for all patients
 - a visit to oncologist (specialty code 65) with RCC as main diagnosis, or
 - In Finland, the ICD-10 codes for metastatic disease are rarely used. In contrast, RCC patients visit oncologist, when and only when disease metastasises and therefore, the visit can be used as a proxy to a metastatic disease.
 - initiation of treatment for mRCC

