7.2.2. Exclusion criteria

For the **characteristics cohort**, patients meeting any of the following criteria will be excluded from the study:

- Prevalent mRCC patients (i.e. diagnosis of metastatic RCC before 1.1.2010)
- Prevalent RCC patients (i.e. diagnosis of RCC before 1.1.2010) if there is no records of metastatic disease during 2010-2021

For the **mRCC cohort**, patients meeting any of the following criteria will be excluded from the study:

- Prevalent patients with mRCC (i.e. diagnosis of metastatic RCC before 1.1.2010)
 - Note that patients with local RCC before 2010 are included in this study if the disease has metastasised during 2010-2021
- Patients without treatment for mRCC (see Table 3 for details)

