7.3. Variables

Source for all variables is the data lake of HDSF.

Table 2. List of study variables. Abbreviations: PO=primary objective, SO=secondary objective.

Variable	Role/Relevant objective	Operational definition
ICD-10 diagnoses; RCC diagnoses	Patient inclusion/exclusion IMDC risk category	yes/no
ICD-10 diagnoses: co-diagnoses (e.g. renal insufficiency and hypertension)	PO1, SO1	yes/no; co-diagnoses before and after index
Date of birth	Patient inclusion PO1	Date; age defined at index based on birth date
Date of death	End of follow-up PO3	Date
Gender	PO1	Female/male
Home municipality	Patient inclusion End of follow-up	Home municipality at each healthcare contact
Weight	PO1	kg
Height	PO1	m
Body mass index (BMI)	PO1	derived from weight and height
Smoking status (if available in structured format)	PO1	yes/no
Outpatient visits (including emergency room visits)	Patient inclusion and index definition (visits to oncologist) SO2	Date, physician's specialty, type of arrival
Hospitalizations	SO2	Start and end dates
Procedures and operations (including nephrectomy)	PO1 SO1 SO2	Procedure code, date
Medical imaging	SO1 SO2	Imaging code, date
Medications; including - hospital medications - prescriptions	Patient inclusion/exclusion and index definition PO2 PO3 SO1 SO2	Dates, ATC-codes, active substance
Laboratory testing	IMDC risk category PO1	Dates, test id, result
Zubrod/ECOG performance status	IMDC risk category PO1	scale 0-5; converted to Karnofsky
PAD histology (if available in structured format)	PO1	
Staging of RCC, the tumor-node-metastasis (TNM) classification	Patient inclusion and index definition PO1	scale 1-4 (stages)

PFIZER CONFIDENTIAL

Table 3. List of medications for RCC treatment. ATC= Anatomical Therapeutic Chemical.

	Active substance	Brand name	ATC-code at the moment in use	ATC-code previously in use
Oral medications	axitinib	Inlyta	L01EK01	L01XE17
	everolimus	Afinitor	L01EG02	L01XE10
	cabozantinib	Cabometyx	L01EX07	L01XE26
	pazopanib	Votrient	L01EX03	L01XE11
	sorafenib	Nexavar	L01EX02	L01XE05
	sunitinib	Sutent	L01EX01	L01XE04
Intravenous medications	ipilimumab	Yervoy	L01XC11	
	nivolumab	Opdivo	L01XC17	

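### The mRCC index can be triggered by only five of the eight drugs that define treated patients, so a patient starting on axitinib, everolimus or sorafenib can be indexed after treatment start or have no index

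*Combined protocol and SAP*

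**What the plan says.** Section 7.2 sets the mRCC index as the "date of the metastatic disease identified as first of the following after the initial RCC diagnosis". There are four triggers. Three do not depend on the drug given: a metastasis code in the range C77–C79, a stage of 4 under AJCC, and an oncologist contact, which counts only if specialty 65 is recorded and RCC is the main diagnosis. The remaining one is a drug start, and it names five substances: "Treatment initiation for mRCC (sunitinib, pazopanib, cabozantinib, ipilimumab, nivolumab".

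Section 7.2.2 removes from the mRCC cohort "Patients without treatment for mRCC (see Table 3 for details". Table 3 in section 7.3, titled "List of medications for RCC treatment", has eight entries. The matching inclusion criterion in section 7.2.1, "initiation of treatment for mRCC", names no drugs.

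Section 7.2.1 also comments on the other triggers. Metastasis codes are seldom used in Finland and AJCC stage may be missing for some patients. The oncologist visit is taken as a proxy because RCC patients are said to see an oncologist if, and only if, the disease has spread.

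**The concern.** Two lists answer what should be one question: which drug starts count as mRCC treatment. Three drugs make a patient treated but cannot date the disease. Followed literally, the rule can place the diagnosis of metastatic disease after the start of its own treatment.

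The index carries a good deal of the analysis:

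- age and residence eligibility (7.2.1);
- characteristics at index (7.7.1);
- the before/after split for co-diagnoses, procedures and medicines, including antihypertensives (6.2, 7.7.4);
- resource use and costs in each of the first five years (7.7.5);
- survival from diagnosis, where that means mRCC diagnosis (6.1, 7.7.3);
- diagnosis year, which is the axis of the coding-practice analysis (7.7.6) and, if mRCC diagnosis is meant, a Cox covariate (7.7.3).

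For a misdated patient, conditions and medicines that arise on treatment are counted as pre-existing, early resource use falls before year 1, and time already survived on treatment is dropped. Because the error depends on which drug came first, it is not random across treatments.

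**Working it through.** **The plan's own figure.** Section 7.5 gives about 1,100 RCC patients, of whom 20–50% develop advanced or metastatic disease. 1,100 × 0.20 = 220 and 1,100 × 0.50 = 550. The stated 220–550 reproduces, and the index rule does not alter it.

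**The two lists.**

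| Source | Drugs | Count |
|---|---|---|
| Index trigger, 7.2 | sunitinib, pazopanib, cabozantinib, ipilimumab, nivolumab | 5 |
| Table 3, 7.3 | the same five, plus axitinib, everolimus, sorafenib | 8 |

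8 − 5 = 3 drugs are in Table 3 only. None is in the index list only.

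**The rule applied to test histories.** Index = earliest trigger after the initial RCC diagnosis. The histories are invented to test the logic. In each, axitinib starts on day 400 after RCC diagnosis.

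| Other records | Index, five-drug list | Index, Table 3 list | Difference |
|---|---|---|---|
| Qualifying oncologist visit, day 390 | 390 | 390 | 0 days |
| First qualifying visit, day 430 | 430 | 400 | 430 − 400 = 30 days late |
| No other trigger until nivolumab, day 640 | 640 | 400 | 640 − 400 = 240 days late |
| No other trigger | none | 400 | no index |

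A late index therefore needs every other trigger to follow the omitted drug. A missing index needs no other trigger at all. A patient who receives an omitted drug only after one of the five listed drugs is unaffected.

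**What does not move.** Section 7.2 re-anchors treatment outcomes at treatment initiation. Section 7.2.3 fixes the IMDC category at the first mRCC treatment. Section 7.7.2 starts each line at the first record of its substance. None of these uses the mRCC index.

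**Number of patients.** The documents do not say how many patients start on an omitted drug. Purely as an assumption, 2–10% of 220–550 would be 0.02 × 220 = 4.4 to 0.10 × 550 = 55. That range counts patients who would depend on the other triggers, not patients misdated. Its base also includes untreated mRCC patients, who cannot start a drug.

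**The case against.** The strongest reply is that the plan already has a safeguard. Its stated answer to rare metastasis coding is the oncologist visit, not the drug list. On the plan's own premise, that visit will usually come before the first drug and set the index. This stands, and it is why the effect is probably small. It does not remove the fault: a visit counts only under specialty code 65 with RCC as main diagnosis, section 7.9 expects missing and erroneous records, and the added drug trigger does not work for three drugs.

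The five drugs might be meant as a first-line list. The protocol does not say so, and its background section names pembrolizumab plus axitinib among the first-line combinations. Pembrolizumab is in neither list, so axitinib is the only component of that regimen in Table 3. This is thin evidence of local use, however: the passage is a general recommendation, and the same section calls combinations problematic under Finnish reimbursement.

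A reader might go further on two points. The first is that a patient with no index is simply included as treated. Section 7.2.1 requires age and residence at index, so such a patient cannot be shown to be eligible, and programming would expose the gap. The second is that a patient who started an omitted drug before 2010 would enter as incident. The prevalent-mRCC exclusion in section 7.2.2 does not cite the five-drug list, so this is an inference. It also needs no other marker before 2010 and a qualifying one later.

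**Conclusion.** The rule is wrong as written. The five-against-eight mismatch is plain in the text and unexplained, and it permits an index after treatment start, or no index, under the conditions shown above. The effect is confined to index-anchored analyses and probably to few patients, on the plan's assumption that oncologist visits reliably mark metastasis. The number misdated cannot be derived from the documents.

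It is tempting to read 3 of 8 drugs (3/8 = 37.5%) as the scale of the problem. That is a share of drug names, not of patients. The 4–55 range is no better as a count of errors, for the reasons given with it. Nor do the documents support a claim that treatment-line results or IMDC strata are distorted. The reason to act is that the definitions conflict and the correction is nearly free, not that a large bias has been shown.

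**What to change.** In section 7.2, replace the five-drug list with the first record of any active substance in Table 3 after the initial RCC diagnosis. Point the treatment criterion in section 7.2.1 to the same list and, for consistency, use it when identifying mRCC before 1.1.2010 under section 7.2.2.

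Add a programmed check that no index in the mRCC cohort is later than the first Table 3 drug record after RCC diagnosis. Running the check under the current rule as well would show how many patients the mismatch affects.

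With this change, no patient whose Table 3 treatment starts after RCC diagnosis can have a late or missing index. The cost is one line of wording and one shared code list. Table 2 already requests the medication data, and the expected cohort size is unchanged.

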4. MILESTONES

Milestone	Planned date
Auria permission and start of data collection	01-May-2022
End of data collection	31-May-2022
The following milestones are dependent on data set completion date. The planned dates have been estimated based on data completion by the end of May 2022:	
Data analyses	01 September 2022
Final study report	01-Nov-2022
Publication submission	To be determined

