5. RATIONALE AND BACKGROUND

Renal cell carcinoma (RCC) is among the 10 most frequently occurring cancers and the most common type of kidney cancer occurring in Western communities [1]. RCCs comprise a heterogeneous group of malignant neoplasms arising from the nephron. Risk factors for RCC include obesity, hypertension, cigarette smoking, diet, diabetes, and male gender [1].

After decades of increasing trends in RCC incidence and mortality rates, it seems that rates are stabilising or starting to decline in many Western countries [1]. The worldwide number of kidney cancer cases was 431,288 (62.9% male) and deaths 179,368 (64.4% male) in 2020 [2]. Kidney cancer is more common in males compared to females. The incidence was 7.8 and mortality 3.0 per 100,000 males in high human development index countries in 2020 [2]. In Finland, the number of new kidney cancer cases was 635 in males and 353 in females in 2019 [3], and the number of prevalent patients was 4,943 males and 3,867 females in 2019 according to the Finnish Cancer Registry [4].

Localized RCC can be curatively treated with nephrectomy. However, about 20–30% of patients present with metastatic RCC (mRCC) at the time of diagnosis [5]. In addition, another 20% of patients with localized RCC undergoing nephrectomy will have a relapse and develop mRCC during follow-up. Despite the recent advances in mRCC treatment, metastatic disease is often fatal [6].

[figure not shown]
Over the last decade, the treatment of advanced/metastatic RCC has been constantly evolving, especially in the last 2-3 years with the emergence of several novel treatment options in rapid succession. Current recommendations for first-line therapy of mRCC include several combination treatments, superseding the previously recommended antiangiogenic agent monotherapies. The novel options combine an anti-PD-1-antibody with either an antiangiogenic drug (vascular endothelial growth factor receptor (VEGFR) tyrosine kinase inhibitor (TKI)), or an anti-CTLA-4-antibody. The combination treatments are recommended

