7.2.3. Patient stratification

Analyses will be stratified by:

- IMDC risk category (defined at the initiation of the first treatment for the metastatic RCC; see Table 1 and listing below for definitions)
 - Applied to all primary and secondary objectives
- Treatment line
 - Applied to primary objective 2 and 3

IMDC risk factors (each criterion accounts for +1 for the risk score):

1. Less than a year from time of initial RCC diagnosis to initiation of treatment for the metastatic RCC

2. Performance status* <80% (Karnofsky)
3. Hemoglobin* below normal (women < 117 g/l; men < 134 g/l)
4. Serum calcium* above normal (> 2.51 mmol/l)
5. Neutrophiles* above normal (> 6.3 x 10⁹/l)
6. Thrombocytes* above normal (> 350 x 10⁹/l)

** for performance status and laboratory values data of ± 3 months around the treatment initiation will be utilized due to possibly sparse data. If multiple records are available, the record closest to the treatment initiation will be utilized.*

Table 1. IMDC risk scores and categories based on two different approaches depending on the data coverage

	IMDC risk category	Total score of IMDC risk factors	Explanations/missing values
Option 1*	Favorable risk	0	no missing values allowed
	Intermediate risk	1-2	1) total score = 1; max 1 risk factor allowed to have missing value 2) total score = 2; no missing values allowed
	Poor risk	3 or more	max 3 risk factors allowed to have missing values
	Unknown risk**	-	when none of the above risk categories can be assigned
Option 2*	Appear favorable	0	all non-missing values for the risk factors indicate favorable risk max 3 risk factors allowed to have missing values
	At least intermediate	≥1	at least one risk factor criterion is met max 3 risk factors allowed to have missing values
	Poor	≥3	at least three risk factor criteria is met max 3 risk factors allowed to have missing values
	Unknown**	-	when none of the above risk categories can be assigned, i.e. more than 3 risk factors have missing value

** If small number of missing values is observed, the option 1 will be selected. If large number of missing values is observed and thus majority of patients were to belong to the “unknown” group of the option 1, the option 2 will be selected. The selection will be done after the data release and monitoring of data coverage.*

*** Patients with unknown risk category, will be analysed as own patient group.*

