7.7.3. Treatment outcomes

Primary objective 3:

The treatment outcomes will be assessed using time-to-event analysis, namely Kaplan-Meier fit or other relevant competing risk models. For each outcome, the time will be defined as follows (Figure 3):

- overall survival:
 - time from index until death (event) or end of study (censoring event)
 - when analysing by treatment lines, start the time from initiation of each treatment line
- progression free survival (PFS, defined using time to next treatment (TTNT) proxy):
 - time from initiation of the current treatment line until the initiation of the next treatment line (event), death (competing risk/event), or end of study (censoring event)

The Kaplan-Meier fits will be visualized, and the median survival/PFS of the patients will be reported as well, if reached.

Additionally, corresponding Cox proportional-hazards model will be fitted, including clinical variables as covariates (including but not limited to age, sex, IMDC risk score, diagnosis year, and treatment line number). The hazard ratios, 95% confidence intervals and p-values corresponding to each covariate will be reported.

[figure not shown]

Figure 3. Graphical illustration of definitions of treatment outcomes. Abbreviations: LOT = line of treatment.

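### Follow-up closes on the last day of inclusion, four to five months before the planned extraction: a cheap loss of precision for recent starters, and an unclear treated/non-treated status for late-2021 patients

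*Combined protocol and SAP*

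**What the plan says.** - **Inclusion.** Section 7.2.1 admits "metastatic RCC during 1.1.2010-31.12.2021; defined as" one of four indicators of advanced disease.
- **End of follow-up.** Section 7.2 takes the earliest of death, an approximated move out of the district, and "End of study (31.12.2021"). Follow-up length counts both end days, so a patient indexed on the last day contributes one day.
- **Outcomes.** Section 7.7.3 defines OS as "time from index until death (event) or end of study (censoring event"). The TTNT proxy for PFS runs from the start of a line to the next line, "death (competing risk/event), or end of study (censoring event").
- **Extraction.** In section 4, "Auria permission and start of data collection" is dated 1 May 2022 and collection ends on 31 May 2022. The later milestones carry the note "The planned dates have been estimated based on data completion by the end of May 2022".
- **Treatment status.** Section 7.2.2 excludes untreated patients from the mRCC cohort. Section 7.7.1 describes treated and non-treated mRCC patients separately.
- **Baseline windows.** Section 7.2.3 says "for performance status and laboratory values data of ± 3 months around the treatment initiation will be utilized due to possibly sparse data". Section 7.7.1 uses 90 days either side of index, extendable to 6 months. Neither section gives a calendar limit.

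The plan gives no reason for stopping before extraction and sets no minimum follow-up. Short follow-up of late entrants is not among the limitations in section 7.9.

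**The concern.** The study wants to describe outcomes over time in a field that section 5 says has changed "especially in the last 2-3 years with the emergence of several novel treatment options in rapid succession". Patients who started treatment in those years have the shortest follow-up, and the common closing date shortens it further, although the data are to be drawn months later.

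Two things are at stake. The first is the number of events behind primary objective 3 (OS and TTNT by treatment line) among recent starters, where events are scarcest. The second is who counts as treated. If drug records also end on 31.12.2021, a patient whose metastasis was found in late 2021 and whose first drug record falls in early 2022 appears among the non-treated in primary objective 1 and is absent from every other objective. That would be misclassification as well as lost information.

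**Working it through.** **Plan's own figure.** Section 7.5 takes about 1,100 RCC patients, of whom 20-50% become metastatic: 1,100 × 0.20 = 220 and 1,100 × 0.50 = 550. This reproduces. The plan gives no event target, power or expected median.

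**Dates.** From last inclusion to end of follow-up: 0 days. From 31.12.2021 to 1 May 2022: 121 days (4.0 months); to 31 May 2022: 151 days (5.0 months). The inclusion window is 4,383 days (144 months).

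**Expected events.** Assumptions, not in the documents: uniform starts, exponential times, median TTNT 8-12 months, median OS 24-36 months. For starts in the last *w* months, *e* extra months of follow-up and median *m*, with λ = ln 2 / *m*:

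P(event) = 1 − [exp(−λe) − exp(−λ(w+e))] / (λw)

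Example, OS with m = 24 and w = 12, so λw = 0.3466:
- e = 0: 1 − (1 − 0.7071)/0.3466 = 0.155
- e = 3: 1 − (0.9170 − 0.6484)/0.3466 = 0.225
- ratio 1.45

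| Starts | Outcome, median (months) | P, e = 0 | P, e = 3 | Gain |
|---|---|---|---|---|
| 2021 | TTNT, 8 | 0.378 | 0.521 | 38% |
| 2021 | TTNT, 12 | 0.279 | 0.393 | 41% |
| 2021 | OS, 24 | 0.155 | 0.225 | 45% |
| 2021 | OS, 36 | 0.107 | 0.157 | 47% |
| 2020-2021 | TTNT, 8 | 0.579 | 0.675 | 17% |
| 2020-2021 | TTNT, 12 | 0.459 | 0.545 | 19% |
| 2020-2021 | OS, 24 | 0.279 | 0.339 | 21% |
| 2020-2021 | OS, 36 | 0.199 | 0.244 | 23% |
| 2010-2021 | TTNT, 8 | 0.920 | 0.938 | 2.0% |
| 2010-2021 | OS, 36 | 0.662 | 0.681 | 2.9% |

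**Absolute numbers, first-line starts.** If all 220-550 patients were treated (an upper bound, since untreated patients are excluded), 2021 starters number 220 × 12/144 = 18.3 to 550 × 12/144 = 45.8.
- Extra deaths: 18.3 × (0.157 − 0.107) = 0.9 to 45.8 × (0.225 − 0.155) = 3.2.
- Extra TTNT events: 18.3 × (0.393 − 0.279) = 2.1 to 45.8 × (0.521 − 0.378) = 6.5.

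**Treatment status.** The documents give no time from mRCC diagnosis to first treatment. If it were 1 to 3 months for everyone (assumption), the patients whose first drug record falls after 31.12.2021 would number 220 × 1/144 = 1.5 to 550 × 3/144 = 11.5, again as an upper bound.

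**Baseline windows.** A 90-day window reaches past 31.12.2021 only for starts after about 2 October 2021: 90/4,383 = 2.1%, or 4.5 to 11.3 patients. The last such window closes on 31 March 2022, before extraction begins.

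**The case against.** Most of the case on the other side stands, and it limits the point.

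- **No bias in the survival estimates.** A fixed administrative cut is non-informative censoring, which Kaplan-Meier and Cox methods handle. A reader might infer biased curves; nothing in the plan supports that.
- **Small base.** The large percentages describe a few dozen patients. The planned outcome analyses pool 2010-2021 by IMDC category and treatment line, with diagnosis year only a Cox covariate. For those the gain is about 2-3%, and the study is primarily descriptive.
- **IMDC window.** A reader might infer that the three-month window is cut off for late starters. The documents do not say so: 31.12.2021 is given as an end of follow-up, not as a limit on laboratory or performance-status records, and Figure 1 is not available. IMDC category is fixed at first treatment, so later lines are untouched. Even with a limit, only about 2% of patients would lose the post-start half of the window. Their pre-treatment records would still count, so few would become unknown.
- **OS medians.** A reader might expect the extension to make OS medians reachable for 2021 starters. Their longest follow-up would rise from 12 to 15 months, still short of the assumed 24-36, and section 7.7.3 already reports medians only if reached.
- **Newest regimens.** Table 3 omits pembrolizumab and lenvatinib, so a later cut would not bring in the combinations that contain them.
- **Completeness.** Recording lag is not stated, and incomplete recent months could introduce error. This may be a sound reason for an earlier cut, but the plan does not offer it.

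None of this explains why follow-up stops four to five months before extraction, or settles how treatment begun in early 2022 is classified.

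**Conclusion.** The point holds as an inexpensive gain in precision and a needed clarification. Inclusion and follow-up end on the same day, extraction is planned 121-151 days later, and no reason is given. Three more months would lift the minimum potential follow-up from one day to about three months. They would add about 2-3% of events overall, 17-23% for 2020-2021 starts and 38-47% for 2021 starts, but at most about 1-3 deaths and 2-7 TTNT events among 2021 first-line starters. These sizes rest on uniform starts, exponential times, the assumed medians and the upper-bound cohort of 220-550 treated patients. The misclassification of treatment status depends on drug records also stopping at 31.12.2021, which the plan neither states nor excludes.

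**What to change.** 1. Keep inclusion to 31.12.2021.
2. Set the administrative end of follow-up for OS, TTNT, treatment status, morbidity and healthcare resource use at 31.3.2022, or at the latest date that Auria Clinical Informatics confirms as complete before extraction. Write that date into the data request.
3. Keep the 31.12.2021 cut as a sensitivity analysis.
4. State that laboratory and performance-status records inside the ±3-month and ±90-day windows are extracted even when dated after 31.12.2021.
5. If 31.12.2021 is kept as the main cut, give the reason, and name short follow-up of late entrants in section 7.9.

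**Cost.** One date in a data request that, at the protocol date of 28 March 2022, was still awaiting permission; no additional patients or procedures. The downside is late registration of the newest entries, which is why the date should precede extraction and be confirmed as complete.
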